We propose to conduct an interventional cross-over study with a cohort of around 100 patients, where initial data is collected without VR for measuring baseline, then VR is implemented twice in a 3-week interval between sessions. We will investigate the impact of VR software on patients' pain and anxiety during the intravenous cannulation procedure, compared with a standard care program. Our primary outcomes involve assessing patient pain and anxiety, while secondary outcomes are fatigue, boredom, and overall patient satisfaction.

Pain and anxiety will be measured both subjectively (VAS) and objectively (cardiac frequency) as secondary exploratory measures. We will also look to assess healthcare providers' and family members' satisfaction levels pre and post VR intervention. The aim of this study is to evaluate the benefits of VR programs in reducing patients' pain and anxiety.

Introduction

Background and Rationale:

Hemoglobinopathies, specifically β -thalassemia, are a significant health concern in the UAE, affecting 8.5% of the population [1,2]. These genetic disorders often require frequent blood draws, chelation therapy, and transfusions, causing stress and impacting quality of life for patients [3].

Repeated pain in children with chronic diseases such as thalassemia can cause behavioural changes in their adolescence, such as anxiety, social problems, and decreased attention. This condition can further impact the quality of life of thalassaemic children as adults [4]. Therefore, nurses must provide specific interventions to improve the child's comfort during invasive procedures.

Virtual reality (VR) is a technology that enables patients to be projected, via a computer system, into an immersive 3-dimensional virtual world. This specificity gives VR a highly immersive and distracting capacity. VR effectively diverts the patient's attention away from the source of pain, thereby diminishing his or her conscious perception of it [5,6].

In recent years, the number of studies investigating the use of Virtual Reality (VR) as a non-pharmacological method of reducing anxiety and pain has grown rapidly. Numerous studies have confirmed this analgesic effect of VR on different modalities such as invasive procedures in chronic diseases such as thalassemia [4,7]. These benefits apply to a multitude of interventions in order to improve the management of pain and/or anxiety, such as wound care [8,9], needle insertion in children [10,11], perioperative management [12,13] and chronic pain relief [14].

Therefore, we propose to conduct an interventional cross-over study to investigate the impact of VR software on patients' pain and anxiety during the intravenous cannulation procedure, compared with a standard care program. The aim of this study is to evaluate the benefits of VR programs in reducing patients' pain and anxiety.

Study Aim:

The primary aim of this study is to assess whether VR has a greater therapeutic impact on patient anxiety and pain perception compared to the standard of care during intravenous cannulation

procedures among thalassemia patients. This study will allow us to conclude on the effectiveness of virtual reality as an adjuvant medical device during the intravenous cannulation procedure.

Study Objectives:

- Evaluate the impact of VR-induced 3D immersion on pain and anxiety during cannulations through visualization of Healthy Mind VR therapeutic sessions.
- Comparison of patients' anxiety levels before and after the procedure with and without VR.
- Comparison of patients' pain levels before and after the procedure with and without VR.

Research Hypothesis:

There will be an improvement in the pain and anxiety measurement parameters with the use of virtual reality during the intravenous catheterisation procedure in thalassemia patients.

Methods:

This is an interventional cross-over, single-center study comparing virtual reality and standard care during intravenous cannulation for thalassemia patients at the Thalassemia Center in Dubai. The study is planned between April 2024 and June 2024.

Participants:

Inclusion criteria:

- Patient with diagnosis of thalassemia
- Thalassemia patient undergoing cannulation intravenous procedure
- Patients aged above >7 years (male, female, adults, paediatric, national and non-national) admitted at the referral center of thalassemia in Dubai

Exclusion criteria:

- Pregnant or nursing woman
- Patient of legal age but subject to legal protection measure or unable to express their consent
- Patient suffering from uncontrolled epilepsy
- Patient with visual or auditory disorders
- Patient suffering from claustrophobia or motion sickness
- Patient with face infection
- Patient with dissociative psychiatric pathologies and autism

After consulting the patients' medical records, and checking that there are no exclusion criteria, the investigators will introduce themselves to the patients and their families, informing them that they are eligible and offering them to take part in the study.

[figure not shown]
Patients will be informed that the study aims to investigate the immersive effect of VR during intravenous cannulation procedure, and they will be provided with a patient information sheet and flyer.

If the patient agrees in principle to take part in the study, and after obtaining informed, signed, written consent, each patient will be given a personalized schedule of the various management appointments and the questionnaires used as part of the protocol.

Interventions:

Patients will benefit from the standard of care for their first visit, then they will have a VR session on their second visit, then another session in VR for their third visit. The VR session starts 5 minutes before the intravenous cannulation procedure, 10 minutes during the procedure and 5 minutes after, for a total of 20 minutes. Before and after the intravenous cannulation procedure, the investigator will complete the Case Report Form for data collection from patients.

All participants will complete questionnaires before and after the procedure at visit 1 (V1), V2 and V3. The interval between visits is 3 weeks, in line with clinical practice at the referral centre.

The two options for managing anxiety and general symptoms are:

1) Standards of care (SOC) :

Thalassemia patients require lifelong monthly blood transfusions to survive. During routine visits, an experienced healthcare provider inserts intravenous cannulation under aseptic technique. Children are escorted by parents to offer support and distraction. This short procedure is accompanied by pain and anxiety for all the involved parties.

2) Virtual reality (VR)

HEALTHY MIND© VR (Paris, France): a 15-minute VR therapeutic session immersing the patient in an artificial world created from computer-generated images using software connected to the PICO 4E headset. The patient can choose one of several types of environments (beach, mountains, lake and others) using synthetic animated images, breathing exercises and advanced psychological/relaxation principles such as cardiac coherence or hypnotic verbal accompaniment.

Variables will be reported in a standardized way in the CRF in the following order:

- Before intravenous cannulation
 - Patient identification number
 - Patient demographics (gender and age)
 - Inclusion and exclusion criteria
 - Patient's VAS for pain intensity
 - Patient's VAS for anxiety
 - Patient's VAS for fatigue
 - Patient's VAS for cramps and heart rate measurement
- After intravenous cannulation:
 - Characteristics of intravenous cannulation. Specificity.
 - Patient's VAS for pain intensity
 - Patient's VAS for anxiety
 - Patient's VAS for fatigue
 - Patient's VAS for cramps and heart rate measurement
 - Patient's VAS for comfort and acceptability of VR headset use

Data collection

	Pre inclusion V0 (*)	Visite 1		Visite 2		Visite 3	
		Before	Post	Before	Post	Before	Post
Screenning and information	✓						
Consent form signed	✓						
Demographic Data ¹		✓					
Physiological data ²		✓	✓	✓	✓	✓	✓
VAS ³ Anxiety, Pain and Fatigue		✓	✓	✓	✓	✓	✓
HAD scale		✓			✓		✓
Patient/Family Satisfaction			✓		✓		
Professional Satisfaction							✓

Expected Outcomes

Primary outcomes: Evaluated by the Visual Analogue Scale (VAS)

- Evaluate the impact of VR-induced 3D immersion on anxiety during cannulations through visualization of Healthy Mind VR therapeutic sessions (using a PICO 4E VR headset). Comparison of patients' anxiety levels before and after the procedure with and without VR. Assessed by visual analog scale (VAS).
- Evaluate the impact of VR-induced 3D immersion pain during cannulations through visualization of Healthy Mind VR therapeutic sessions (using a PICO 4E VR headset). Comparison of patients' pain levels before and after the procedure with and without VR.

Secondary outcomes: Evaluated by the Visual Analogue Scale (VAS)

- Evaluation of fatigue levels after the procedure for patients with and without VR.

- Examine factors associated with boredom and weariness with and without VR.
- Evaluation of patient satisfaction with and without VR.
- Assessment of healthcare professionals' satisfaction levels during and after the procedure with and without VR.
- Assessment of family members' satisfaction levels during and after the procedure with and without VR.
- Assessment of other outcomes of interest (exploratory)
 - Evaluation of the heart rate with and without VR (cardiac frequency)

Sample size calculation:

Due to the exploratory nature of the study, the sample size was calculated on the basis of the number of possible orders of relaxation sessions, which was calculated as follows: 3 types of options x 3 x 2 = 18 possible session orders.

At least two different patients had to be enrolled for each type of option (i.e. 36 patients), to ensure a homogeneous distribution of the different possible orders of relaxation within the study population. 100 patients had to be enrolled in the study, to take account of patients lost to follow-up and missing data. Study power was set at 80% to demonstrate a clinically significant difference greater than 2, with an alpha threshold of 0.05.

Statistical analysis of primary objectives:

The difference between two sessions (VR vs SOC) will be followed by a comparison of the proportions of patients who achieved at least a 25% improvement in anxiety, pain, fatigue, and depression, assessed by the VAS and HAD scale in post-cannulation procedure. The value provided to patients in the VR session during intravenous cannulation procedure and patients with SOC, will be compared using Student's t-test, after verification of the homoscedasticity hypothesis by a Levene's test.

If this hypothesis is not verified, the Mann-Whitney test will be performed, for which the number of patients required to maintain 90% power is 35 per group. If the reduction is not 25% but only 20%, with a power of 80%, this difference will be highlighted.

A 2-factor repeated-measures ANOVA model (VR vs. non-VR session and time before vs. time after) will be developed. Another statistical model will be developed, in order to see the time and session effect and to see if there is an interaction between the 2 factors. Finally, the correlation between basal anxiety scores on the different VAS, HAD scales will be estimated using Pearson's or Spearman's coefficients; the same statistical approach will be used to assess correlations between basal anxiety and their levels measured after the cycles by the VAS.

Statistical analysis of secondary objectives:

The difference between two sessions (VR vs SOC) will be followed by a comparison of the proportions of patients who achieved at least a 25% improvement in satisfaction, assessed by the VAS. Comparison will be carried out using the same method used for primary objectives.

Risk factors associated with dissatisfaction will be explored using uni and multivariate logistic regression models.

Overall ethical considerations

This study is useful both for its scientific contribution and for improving the comfort of thalassemia patients undergoing invasive procedures such as intravenous cannulation. Through this study, we will gain insight into the impact of virtual reality as an adjuvant to care for intravenous cannulations.

Our research will be conducted in accordance with the Declaration of Helsinki and the National Act on Research Involving Human Subjects. We will ensure that no coercion or pressure to participate is exerted on patient-participants. Written informed consent will be obtained from each participant. At any time and without explanation, participants may leave the study without any effect on future care, treatment or working conditions.

With the exception of necessary personal data (socio-demographic information), members of the research team will maintain confidentiality with patient information. Participant data will be anonymised or coded as appropriate and stored securely.

Limitations

A limitation of our study is that randomising the order of intervention sessions was not favourable for our investigation. Because our participants all suffer from chronic disease, the most appropriate way to get a baseline for pain and anxiety perception is before exposure to VR intervention. If done in an alternative manner, i.e. starting with a VR session and then not having VR, it would be more likely for patients to over-report their feelings of pain or anxiety, thus skewing the results. Hence, ordering the sessions in the way that was ultimately decided was, we believe, in favour of reducing bias.

The results of this study will be applicable to all population groups which do not fall under our exclusion criteria (as mentioned in the methods).

Project Timeline

	Feb 2024	Mar 2024	15th April – 15th June	July 2024	Aug 2024	Nov-Dec 2024
IRB Submission						
Site preparation, staff training						
Screening and inclusion						
Data management						
Statistical analysis						
Dissertation writing						

Acknowledgements

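### The primary outcomes target pain and anxiety during cannulation, but the visible VAS items and the stated primary comparison cover only before and after, so the VR effect at the needle may be misstated

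*Combined protocol and SAP*

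**What the plan says.** All references are to the combined protocol and SAP.

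- **Target.** The first item under Study Objectives is "Evaluate the impact of VR-induced 3D immersion on pain and anxiety during cannulations". The Study Aim and both primary outcomes (Expected Outcomes) also place the question during cannulation.
- **Primary comparison.** For pain, Expected Outcomes gives "Comparison of patients' pain levels before and after the procedure with and without VR". For anxiety it gives "Comparison of patients' anxiety levels before and after the procedure with and without VR. Assessed by visual analog scale (VAS".
- **Data collected.** The CRF list under Interventions has "Patient's VAS for pain intensity", a matching anxiety item and "Patient's VAS for cramps and heart rate measurement", once in the block before cannulation and once in the block after. In the Data collection table the row "VAS ³ Anxiety, Pain and Fatigue" has only Before and Post columns at V1, V2 and V3.
- **Analysis.** The section on primary objectives states: "A 2-factor repeated-measures ANOVA model (VR vs. non-VR session and time before vs. time after) will be developed". The same section plans a comparison of the VR and standard-care (SOC) sessions and a 25% improvement criterion assessed post-cannulation.
- **Timing.** Under Interventions, VR runs 5 minutes before, 10 minutes during and 5 minutes after the procedure. The minute of the after rating is not given.

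**The concern.** Needle pain is brief. A rating of pain before the needle precedes the event that VR is meant to blunt. A rating afterwards, unless its prompt points back to the insertion, records what remains. The change between the two then leaves out the period that the objective names.

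Interpretation is at stake in both directions. A null result could not be read as showing that VR fails to reduce pain during cannulation, and a positive one could describe the state afterwards. The session-by-time interaction in the ANOVA inherits the problem. The 25% improvement criterion, if applied to change from the pre-needle pain score, is undefined when that score is 0 and unstable near 0. Anxiety may be affected too, but the argument from brief needle pain does not carry over to it automatically.

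**Working it through.** **1. Target against measure**

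| Element | Period covered |
|---|---|
| Study Aim, first objective, both primary outcomes | During cannulation |
| Second and third objectives | Before and after |
| Comparison stated within each primary outcome | Before and after |
| CRF items and Data collection table (VAS, physiological data) | Before and after |
| ANOVA time factor | Before and after |

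No visible item has a during time point or a recall period. The VAS entries appear under the same names in both CRF blocks. A pre-needle rating cannot look back on the needle, so the pair reads most naturally as one state measured twice.

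**2. The plan's own figure**

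The sample size section gives 100 patients, 80% power, a difference greater than 2 and alpha 0.05, but no SD, so the 100 cannot be reproduced. It can only be inverted. For a paired, two-sided comparison (normal approximation):

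SD of differences = 2 × √100 / (1.960 + 0.842) = 7.14

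This gives no information on how much of a procedural effect survives to the after rating.

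**3. Sensitivity range**

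Assumptions, none taken from the documents: 0–10 VAS; true VR effect of 2 points at the needle; a fraction f of it present at the after rating; SD of the within-patient VR–SOC difference from 2.5 to 5; two-sided 0.05. With n = 100 pairs, power is that of the paired t-test with 99 degrees of freedom and noncentrality

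2 × f × √100 / SD

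Example: f = 0.5 and SD 4 give 2 × 0.5 × 10 / 4 = 2.5, hence power 0.697.

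| SD of differences | f = 1 (2 points) | f = 0.5 (1 point) | f = 0.25 (0.5 point) |
|---|---|---|---|
| 2.5 | >99% | 98% | 51% |
| 3 | >99% | 91% | 38% |
| 4 | >99% | 70% | 24% |
| 5 | 98% | 51% | 17% |

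The smallest f that keeps 80% power is (1.960 + 0.842) × SD / (2 × √100), which is 0.35, 0.42, 0.56 and 0.70 for SDs of 2.5, 3, 4 and 5.

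The expected estimate is 2f whatever the SD: 1.0 point at f = 0.5 and 0.5 point at f = 0.25.

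**4. Direction**

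Dilution assumes the same delay between needle and rating at every visit. If staff rate after VR ends at V2 and V3 but straight after the procedure at V1, the VR rating falls about 5 minutes further from the needle, pain has longer to fade, and the VR effect is overstated. The plan does not exclude this. It also describes the VR session elsewhere as 15 minutes against the 20-minute total under Interventions. The two must be reconciled before the delay can be known.

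**The case against.** The strongest reply is that the VAS prompt cannot be seen. The CRF list gives variable names only, and the VAS footnote and the appendix content are not shown. A scale completed after a procedure can ask about that procedure. This stands: a reader might infer that the plan records current pain and never asks about the needle, but the documents do not show that. If the prompt is retrospective, the objection falls for the post-procedure VAS values, although the before versus after contrast would then set two different quantities against each other.

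The wording of the target is mixed, since the second and third objectives name before and after levels. The analysis section also already plans a VR versus SOC comparison, in a sentence that mentions the cannulation procedure. Both points are fair. They soften the mismatch, but no visible CRF item supplies a value for the insertion itself.

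A reader might also infer that the trial is underpowered or bound to understate the effect. Neither is supported. The SDs and persistence fractions are assumed, and at 100 patients with SD 2.5, half persistence still leaves 98% power. The low value at half persistence with that SD (0.646) arises only at n = 36, a count derived from session orders and not the enrolment target. The bias could also run the other way.

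Heart rate is exploratory, so its timing does not bear on the primary comparison. Finally, recall has its own weakness: it may differ between a distracted and an undistracted session.

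**Conclusion.** The point holds in limited form. The aim and both primary outcomes concern the procedure, while the visible measurements and the stated primary comparison describe change from a pre-needle state to a post-procedure state. Nothing visible links the after rating to the insertion. The result may therefore misstate the VR effect on procedural pain, and possibly anxiety.

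Dilution is the likelier direction for pain, and overstatement is possible while the rating minute is open. The size is conditional on the assumptions above. Loss of power ranges from negligible to severe, but for any f of one half or less the estimate would be at most 1.0 point, so a true 2-point effect could be judged clinically unimportant even when statistically significant. The plan should be changed on this point. Confidence is medium because the prompt is not visible.

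**What to change.** - In the CRF list and primary outcomes, word the post-procedure VAS items as worst pain and highest anxiety felt during the needle insertion. Ask them identically, and at the same stated time after insertion, at V1, V2 and V3. If the existing prompt already does this, state it in the outcome definition.
- Make the within-patient VR–SOC difference in these ratings the primary comparison, and state how V2 and V3 enter it. This builds on the session comparison already planned.
- Use the pre-procedure VAS, recorded before VR starts, as a covariate and not as one half of a before/after change.
- A heart rate reading at insertion is optional.

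The cost is one sentence per VAS item, a fixed rating time and an edit to the analysis section, with no extra visit, instrument or patient. The downside is recall over a few minutes, which VR distraction could itself influence. This should be acknowledged as a limitation.

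### The stated basis for the sample size, 18 session orders, does not exist in this one-cohort, fixed-order design, and the 80% power claim lacks the inputs needed to check it

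*Combined protocol and SAP*

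**What the plan says.** **Sample size calculation.** N is said to come from the number of possible orders of the relaxation sessions: "3 types of options x 3 x 2 = 18 possible session orders". The next step is "At least two different patients had to be enrolled for each type of option (i.e. 36 patients"), so that the orders are spread evenly over the patients. Then "100 patients had to be enrolled in the study, to take account of patients lost to follow-up and missing data". The paragraph closes with 80% power for a clinically significant difference above 2 at alpha 0.05.

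**Design.** The opening summary describes "a cohort of around 100 patients, where initial data is collected without VR for measuring baseline, then VR is implemented twice". Interventions says "Patients will benefit from the standard of care for their first visit, then they will have a VR session on their second visit", with VR again at the third visit. It introduces SOC and VR with "The two options for managing anxiety and general symptoms are". Within VR, "The patient can choose one of several types of environments (beach, mountains, lake and others"). Limitations says "A limitation of our study is that randomising the order of intervention sessions was not favourable for our investigation" and defends the fixed order.

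**Statistical analysis of primary objectives.** If the equal-variance check fails, a Mann-Whitney test is used, with 35 per group said to keep 90% power. The next sentence mentions a reduction of 20% instead of 25%, with 80% power.

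**The concern.** The sample size paragraph describes a trial with several session types given in varying orders. The rest of the protocol describes a single sequence. If the stated reason for N is a feature the trial lacks, then N has no documented basis. The power sentence does not fill the gap, because it gives a difference and an alpha and nothing else.

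What is at stake is interpretation. A reader cannot tell what difference in pain or anxiety, or in the proportion of responders, 100 patients can detect. A null or small result therefore cannot be read against the plan.

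**Working it through.** **1. The order count against the design**

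| | Sample size calculation | Rest of the protocol |
|---|---|---|
| Options | 3 types | 2 (SOC, VR) |
| Orders | 3 x 3 x 2 = 18 | 1 (SOC, VR, VR) |
| Purpose | spread the orders evenly | order deliberately not randomised |

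The products themselves reproduce: 3 x 3 x 2 = 18 and 2 x 18 = 36. The VR environments do not supply the three types. The list is open, the patient chooses from it, and visit 1 has no VR.

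**2. The 36.** The text attaches two patients to each type of option. Two for each of three options is 2 x 3 = 6, and for the two options in the design it is 2 x 2 = 4. Only two per order gives 36.

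**3. From 36 to 100.** No loss rate is given. Enrolment for a loss rate d is 36/(1 - d):
- 10%: 36/0.9 = 40
- 20%: 36/0.8 = 45
- 30%: 36/0.7 = 51.4, so 52

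If 36 were the evaluable target and loss the only reason for the increase, 100 would imply 1 - 36/100 = 64%.

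**4. The 80% power.** Inputs given: difference 2, alpha 0.05. Assumed here: paired t-test, two-sided. The SD is that of the within-patient contrast and is varied, because the documents give none. Power comes from the noncentral t distribution with n - 1 degrees of freedom and noncentrality (2/SD) x sqrt(n).

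The standardised difference d that gives 80% power is 0.4802 at n = 36 and 0.2829 at n = 100. The SD at which the claim holds exactly is 2/d:
- n = 36: 2/0.4802 = 4.16
- n = 100: 2/0.2829 = 7.07

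| Contrast SD (assumed) | Power, n = 36 | Power, n = 100 |
|---|---|---|
| 4 | 83% | >99% |
| 5 | 65% | 98% |
| 6 | 49% | 91% |
| 7 | 39% | 81% |

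The VAS range is also missing, and it decides the answer.
- *Assumed 0-10 scale.* A score SD is at most about 5. With non-negative correlation between visits, the difference in post-procedure scores has SD at most 5 x sqrt(2) = 7.07. At that bound, power is about 80% with 100 evaluable, 76% with 90 and 71% with 80. The bound does not cover a contrast of before-after changes.
- *Assumed 0-100 scale, contrast SD 20 to 30.* With 100 evaluable, power for 2 points is about 17% to 10%.

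**5. The 35 per group.** This appears in the analysis section, not as a basis for N. Mann-Whitney compares two independent groups. Here every patient has both conditions, so no such groups exist. The remark is also not linked to the 80% stated for the main calculation.

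**6. The 25%/20% sentence.** The documents give no reference rate, mean or SD, so two readings were tried.
- *Mean effects proportional to the reduction, same SD, 35 per group.* 90% power needs d = 0.786. At 0.8 x 0.786 = 0.629, power is about 74%, which does not match 80%.
- *Differences in proportions from an assumed 0% reference rate, pooled two-proportion formula, two-sided 0.05.* A 25-point difference at 90% needs 34.65 per group, and a 20-point difference at 80% needs 34.12. Both round up to 35, so both match.

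The sentence can be made to fit or not, depending on inputs the plan does not state.

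**The case against.** **The study is called exploratory.** It is, and an exploratory trial may fix N by feasibility. But the same paragraph says N was calculated from orders and claims 80% power for a clinically significant difference, and the study aim promises a conclusion on effectiveness. The label does not create 18 orders.

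**100 may well be enough.** This stands. On an assumed 0-10 VAS, 100 evaluable patients give about 80% or more for a 2-point post-procedure difference up to the SD bound. A reader might infer that the trial is underpowered, but the documents give no SD or scale on which to say so. Nor do they support reassurance, since the assumed 0-100 case points the other way.

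**36 is a minimum, and missing data are named as well as loss.** This stands. The 64% is conditional and should not be quoted as the plan's own loss assumption. What can be said is that no rate is given and the step is unexplained.

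**The 35 per group is not the basis for N.** Correct. It is a separate remark in the analysis section, and its fault is the assumption of independent groups.

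**The 25%/20% sentence is ambiguous.** This also stands. A reader might infer that its 80% is wrong because one reading gives 74%. The proportions reading reproduces both figures at 35, so an error is not shown. That match depends on the 0% rate: at 5% the needs are 47 and 49 per group. Mann-Whitney is also not a test of proportions. The sentence is undocumented, not shown to be wrong.

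**Conclusion.** Wrong as written. The text alone settles three points. The stated basis for N (18 orders, 36 patients) is contradicted by the single fixed order. The 36 does not follow from two patients per option. The 35 per group refers to groups that do not exist.

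The step from 36 to 100 has no stated rate. The 80% power is unsupported, not shown to be false: for 2 points it is exact only at a contrast SD of 4.16 (n = 36) or 7.07 (n = 100), on the assumption of a paired, two-sided test. The other power figures rest on assumed scales and SDs and only show how far the answer moves. The finding is that N cannot be traced, not that it is too small.

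**What to change.** Keep 100 enrolled. Delete the order count, the 36, the 35 per group and the 25%/20% power sentence. Replace them with a statement labelled *detectable difference at fixed N*, given separately for pain and for anxiety, that names:
- the VAS range;
- the within-patient contrast: post-procedure score or before-after change, and which VR visit is compared with visit 1;
- sidedness;
- an assumed SD range for that contrast;
- an expected loss rate.

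At two-sided 0.05 and 80% power, paired t-test:

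| Evaluable | Detectable difference | Example: assumed SD 3 |
|---|---|---|
| 100 | 0.283 x SD | 0.85 points |
| 90 | 0.299 x SD | 0.90 points |
| 80 | 0.317 x SD | 0.95 points |

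State that the comparison of patients with at least 25% improvement is not powered. A paired-proportion (McNemar) figure is optional and would need an assumed share of discordant patients.

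The cost is protocol and SAP wording only, with no extra patients, visits or data. The downside is that the SD range and loss rate must be declared as assumptions, and the plan can then claim only a detectable difference, not a derived N.
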